7.3.5. Other Objective Response Rates

The ORR in Cohort B is defined as the proportion of participants in Cohort B who achieve a BOR of CR or PR, based on RANO (Wen et al 2010) and assessed by an ICR. It will be estimated with its 95% CI using the Clopper-Pearson method.

The ORR in Cohorts A and B combined is defined as the proportion of participants in Cohorts A and B who achieve a BOR of CR or PR, it will be based on RANO ([Wen et al 2010](#)) and assessed by an ICR. It will be estimated with its 95% CI using the Clopper-Pearson method.

The ORR in Cohorts A and B will be based on RANO ([Wen et al 2010](#)) and assessed by the investigator. It will be estimated with its 95% CI using the Clopper-Pearson method

7.4. Other Efficacy Analyses

7.4.1. Largest Percentage Reduction in Sum of Products of Perpendicular Diameters

For each participant in the FAS with measurable enhancing lesions at baseline, measurable enhancing lesion size will be measured by the sum of the products of the perpendicular diameters of all measurable enhancing lesions. The best percent change from baseline, defined as the largest decrease in measurable enhancing lesion size for each participant, will be summarized descriptively, and a waterfall plot of the best percent change will be generated. Note that for participants who only have increases in measurable enhancing lesion sizes from baseline, the smallest increase will be considered as the best change from baseline.

Per RANO criteria, a lesion deemed "too small to measure" will be assigned a value of 5 mm, for an axis that falls below the "too small to measure" threshold of 5 mm. For example, if both axes of measurable enhancing lesions are considered "too small to measure," then the lesion will be assigned a default value of $5 \times 5 \text{ mm}^2$ for purposes of analysis. If only 1 axis falls below the "too small to measure" threshold, then only that measurement will be assigned a value of 5 mm.

Likewise, measurable enhancing lesions identified as "not present" at postbaseline assessments will be assigned $0 \times 0 \text{ mm}^2$ for this analysis. In the event a measurable enhancing lesion is unaccounted for in a particular postbaseline timepoint (ie, assessment missing or NE), then the overall sum of products of perpendicular diameters for measurable enhancing lesions will not be evaluable for that postbaseline timepoint.

7.4.2. NANO Scale

The NANO scale is a disease-specific clinician-reported outcome assessment tool to measure neurological function across 9 relevant neurologic domains most relevant to participants with intracranial malignant tumors (ie, gait, strength, upper extremity ataxia, sensation, visual fields, facial strength, language, level of consciousness, and behavior; [Nayak et al 2017](#)). Relevant and discrete levels of function were defined for each neurological domain (see [Appendix B](#)).

The NANO scale provides an objective and quantifiable metric to score neurological function at each planned study visit. Moreover, it objectively defines clinical parameters of response and progression related to underlying tumor activity. When the NANO is combined with the radiological disease assessment, the result generates a robust measure of outcome for patients.

A total NANO score is generated at each scheduled assessment. The NANO scale for each domain at the scheduled assessment times will be summarized and listed. For the total NANO score, baseline value, postbaseline value, and change from baseline will be summarized descriptively by planned study visits.

7.5. Analysis of Exploratory Efficacy Variables

7.5.1. Karnofsky Performance Status Score

[figure not shown]
The Karnofsky Performance Status is a standard way of measuring the ability of participants with cancer to perform ordinary tasks. The scores range from 0 to 100 (see [Table 3](#)) and will be assessed at scheduled assessment times. It is recommended, when possible, that a participant's performance status is assessed by the same person throughout the study.

[figure not shown]
The Karnofsky Performance Status scores and changes in status at scheduled assessment times will be summarized. Shift tables will be presented showing change in Karnofsky Performance Status scores from baseline to worst postbaseline score.

Table 3: Karnofsky Performance Status Scores

Score	Performance Status
100	Normal, no complaints; no evidence of disease.
90	Able to carry on normal activity, minor signs or symptoms of disease.
80	Normal activity with effort, some symptoms or signs of disease.
70	Cares for self; unable to carry on normal activity or to do active work.
60	Requiring occasional assistance, can take care of most personal requirements.
50	Requires considerable assistance, requires frequent medical care.
40	Disabled, requires special care and assistance.
30	Severely disabled, hospital admission indicated but no risk of death.
20	Very ill, urgently requiring hospital admission, requires supportive measures or treatment.
10	Moribund; fatal processes progressing rapidly.
0	Dead.

Source: [Terret et al 2011](#).

8. SAFETY AND TOLERABILITY

[Appendix A](#) provides a list of data displays. Sample data displays are included in a separate document.

8.1. General Considerations

The analyses in this section will be provided for the safety population. Summary tables may be replaced with listings when appropriate. For instance, an AE frequency table may be replaced with a listing if it only contains a few unique preferred terms reported on relatively few participants.

8.2. Adverse Events

8.2.1. Adverse Event Definitions

A TEAE is any AE either reported for the first time or worsening of a pre-existing event after the first dose of study drug until 30 days after the last dose of study drug. Analysis of AEs (as discussed below) will be limited to TEAEs, but data listings will include all AEs regardless of their timing in relation to study drug administration. For purposes of analysis, all AEs will be considered TEAEs unless the AE can unequivocally be defined as not treatment-emergent.

Adverse events will be tabulated by MedDRA PT and SOC. Severity of AEs will be graded using the NCI CTCAE v5.0. The CTCAE reporting guidelines and grading details are available on the Cancer Therapy Evaluation Program website.

A grading (severity) scale is provided for each AE term. If the toxicity is not included in the CTCAE v5.0 criteria, it will be graded on a scale of 1 to 5 as follows: 1 = mild, 2 = moderate, 3 = severe, 4 = life-threatening, and 5 = fatal. All toxicities will be graded based on the worst level reached, not the level they may have reached if they had not been treated. When the intensity of an AE changes over time for a reporting period (eg, between visits), each change in intensity will be reported as an AE until the event resolves.

The subset of AEs considered by the investigator to be related to study drug will be considered to be treatment-related AEs. If the investigator does not specify the relationship of the AE to study drug, the AE will be considered to be treatment-related. The incidence of AEs and treatment-related AEs will be tabulated. In addition, serious TEAEs will also be tabulated.

Any missing onset date, causality, or severity must be queried for resolution. Unresolved missing causality and severity will be handled according to the following rules:

- An unresolved missing causality will be considered treatment-related.
- An unresolved missing severity will be identified as an unknown severity.

8.2.2. Clinically Notable Adverse Events

Specific groupings of clinically notable AEs will be considered and the number of participants with at least 1 event within each grouping will be reported. Such groups consist of AEs for which there is a specific clinical interest in connection with pemigatinib or AEs that are similar in nature (although not identical). The groups are defined in [Table 5](#). All clinically notable AEs are defined through PTs, as per the current MedDRA v26.0.

Table 5: Clinically Notable Adverse Events by Grouping

Categories	Preferred Terms
Serous retinal detachment	Serous retinal detachment, detachment of macular retinal pigment epithelium, detachment of retinal pigment epithelium, retinal detachment, subretinal fluid, chorioretinopathy, retinal pigment epitheliopathy, chorioretinal disorder, retinopathy, maculopathy, retinal disorder, retinal thickening, chorioretinal folds, chorioretinal scar
Nail toxicity	Nail toxicity, nail bed tenderness, nail bed disorder, nail bed bleeding, nail disorder, nail discolouration, nail discomfort, nail dystrophy, nail hypertrophy, nail ridging, nail infection, onychalgia, onychoclasia, onycholysis, onychomadesis, onychomycosis, paronychia, fungal paronychia
Hyperphosphatemia	Hyperphosphataemia, blood phosphorus increased
Hypophosphatemia	Hypophosphataemia, blood phosphorus decreased
Dry eye	Dry eye, meibomian gland dysfunction, lacrimation increased, keratitis, punctate keratitis, pinguecula, pterygium
Eyelash changes	Eyelash changes, growth of eyelashes, trichiasis, trichomegaly
Vision blurred	Vision blurred, visual impairment, visual acuity reduced
Vitreous detachment	Vitreous detachment, vitreous floaters

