2.3. Benefit/Risk Assessment

Targeted therapies with a manageable safety profile that can provide a durable response or significant disease control in a molecularly defined population would provide a meaningful clinical benefit. To date, pemigatinib has been administered to over 900 patients across 7 Incyte-sponsored clinical trials and commercially ([Pemazyre 2021a](#), [Pemazyre 2021b](#)); it has an established clinical benefit in cholangiocarcinoma as well as a robust safety profile. In an earlier clinical trial (Study INCB 54828-207), pemigatinib was tested in several participants with GBM and showed a favorable risk/benefit ratio for further development in this population.

The most frequently reported TEAEs associated with pemigatinib use includes HP, nail toxicity, and hypophosphatemia. Rare but significant AEs associated with pemigatinib use include SRD and soft tissue mineralization including calcinosis and calciphylaxis.

Overall, the efficacy and safety data from the pemigatinib clinical development program to date show a favorable benefit/risk ratio for pemigatinib treatment in patients with FGFR2 rearranged solid tumors.

More detailed information about the known and expected benefits and risks and reasonably expected AEs of pemigatinib may be found in the [IB](#).

[figure not shown]

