| b | Hemoglobin | $\leq 9 \text{ g/dL}$ (transfusion allowed with a 2-week washout period) |
| c | ANC | $\leq 1.5 \times 10^9/\text{L}$ |
| Hepatic | | |
| d | ALT | $\geq 3 \times \text{ULN}$ ($> 5 \times \text{ULN}$ for liver metastasis) |
| e | AST | $\geq 3 \times \text{ULN}$ ($> 5 \times \text{ULN}$ for liver metastasis) |
| f | Total bilirubin | $\geq 1.5 \times \text{ULN}$ ($\geq 2.5 \times \text{ULN}$ if Gilbert's syndrome or liver metastasis) |
| g | Alkaline phosphatase | $\geq 3 \times \text{ULN}$ |
| Renal | | |
| h | Serum creatinine clearance | $\leq 30 \text{ mL/minute}$ based on Cockcroft-Gault formula |
| Chemistry | | |
| i | Serum phosphate | $> \text{ULN}$ |
| j | Serum calcium | Outside of normal range or serum albumin-corrected calcium outside of the normal range when serum albumin is outside of the normal range |

12. History of calcium and phosphate homeostasis disorder or systemic mineral imbalance with ectopic calcification of soft tissues (exception: commonly observed calcifications in soft tissues such as the skin, kidney tendon, or vessels due to injury, disease, or aging in the absence of systemic mineral imbalance).
13. Significant gastrointestinal disorder(s) that could interfere with absorption, metabolism, or excretion of study drug.
14. Clinically significant or uncontrolled cardiac disease including unstable angina, acute myocardial infarction within 6 months before Day 1 of study drug administration, New York Heart Association Class III or IV congestive heart failure, and uncontrolled arrhythmia (participants with pacemaker or with atrial fibrillation and well controlled heart rate are allowed).
15. History or presence of an abnormal ECG that, in the investigator's opinion, is clinically meaningful. A screening QTcF interval > 480 milliseconds is excluded. For participants with an intraventricular conduction delay (QRS interval > 120 ms), the JTc interval may be used in place of the QTc with medical monitor approval. The JTc must be ≤ 340 milliseconds if JTc is used in place of the QTc.
16. Active chronic or current infectious disease requiring systemic antibiotic, antifungal, or antiviral treatment within 2 weeks before enrollment (participants with asymptomatic chronic infections on prophylactic treatment are allowed).

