6.6.1. Restricted Medications and Procedures

Pemigatinib is predominantly metabolized by CYP3A4. There is an expected 50% increase in exposure in participants who concomitantly use CYP3A4 moderate inhibitors. However, as doses above the recommended Phase 2 dose of 13.5 mg QD have been tested (20 mg QD is tolerable), there is a sufficient safety margin. The use of moderate CYP3A4 inhibitors (see [Appendix D](#)) should be avoided; however, if unavoidable, the pemigatinib dose should be reduced from 13.5 mg to 9 mg or from 9 mg to 4.5 mg. If concomitant use of a moderate CYP3A inhibitor is discontinued, the pemigatinib dose can be increased (after 3 plasma half-lives of the CYP3A inhibitor) to the dose that was administered before starting the moderate inhibitor. The use of potent CYP3A4 inhibitors and inducers are prohibited (see Section [6.6.2](#)).

In certain instances, palliative surgery or radiotherapy to specific lesions is permitted if considered of benefit and medically necessary by the investigator. The sponsor must be notified if palliative surgery or radiotherapy is started; for any palliative radiotherapy or non-disease-related surgeries, the medical monitor should be consulted on when to restart pemigatinib. The lesions treated with palliative surgery or radiotherapy can no longer be assessed as target lesions.

In general, investigators should manage a participant's care with supportive therapies as clinically indicated, per local standard practice. However, care should be taken to assess any concomitant medication for the potential to have adverse drug-drug interactions with study treatment, including potentially impacting CYP3A4 metabolism.

Careful monitoring is required when pemigatinib is concomitantly administered with OCT2 substrates such as dofetilide and metformin, mild or moderate CYP3A4 inhibitors or inducers, and proton pump inhibitors.

Calcium-based phosphate-binding medications should not be used due to a concern for soft tissue mineralization. Refer to the [IB](#) for further details.

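### SAP Table 5 has no group for soft tissue mineralization, so no participant-level pooled count of this named pemigatinib risk is planned, although its individual preferred terms are tabulated and listed

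*SAP*

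**What the plan says.** SAP 8.2.2 sets up groups of clinically notable adverse events. It describes them so: "Such groups consist of AEs for which there is a specific clinical interest in connection with pemigatinib", or events that are alike in nature without being identical. For these groups, "the number of participants with at least 1 event within each grouping will be reported". Table 5 defines the groups through MedDRA v26.0 preferred terms. There are eight: serous retinal detachment, nail toxicity, hyperphosphatemia, hypophosphatemia, dry eye, eyelash changes, vision blurred and vitreous detachment.

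SAP 8.2.3 and Appendix A then plan six grouped tables, 3.2.21 to 3.2.26 (any event, Grade 3 or higher, serious, and leading to dose reduction, interruption or discontinuation), plus Listing 2.7.7.

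Protocol 2.3 states the known risks in two sentences: "The most frequently reported TEAEs associated with pemigatinib use includes HP, nail toxicity, and hypophosphatemia", and "Rare but significant AEs associated with pemigatinib use include SRD and soft tissue mineralization including calcinosis and calciphylaxis". Mineralization returns twice as a working concern. Protocol 6.6.1 says: "Calcium-based phosphate-binding medications should not be used due to a concern for soft tissue mineralization". Exclusion criterion 12 in Protocol 5.2 begins: "History of calcium and phosphate homeostasis disorder or systemic mineral imbalance with ectopic calcification of soft tissues", with an exception for commonly seen calcifications that arise from injury, disease or aging without systemic mineral imbalance.

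**The concern.** The groups exist so that a risk coded under several preferred terms can be read as one number of participants. That matters most for rare events, where each term may hold only one or two people. The protocol treats mineralization as a specific pemigatinib risk in its benefit-risk statement, its eligibility rules and its concomitant-medication rules, so it fits the SAP's own description of what the groups contain. Table 5 nevertheless leaves it out, while including dry eye, eyelash changes and vitreous detachment, which Protocol 2.3 does not name.

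At stake is the clarity of one safety summary. If cases occur, the study report would have no planned line saying how many participants had any mineralization event, how many of those were Grade 3 or higher or serious, and how many led to a change in dosing. If terms were chosen for pooling only after the events had been seen, the choice would be open to question.

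**Working it through.** The plan gives no figure on this point, so there is none to reproduce. The check is mainly a comparison of texts.

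**Step 1: match the risks in Protocol 2.3 to SAP Table 5.**

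| Risk in Protocol 2.3 | How the protocol describes it | Group in Table 5 |
|---|---|---|
| Hyperphosphatemia | most frequent | yes |
| Nail toxicity | most frequent | yes |
| Hypophosphatemia | most frequent | yes |
| Serous retinal detachment | rare but significant | yes (14 preferred terms) |
| Soft tissue mineralization | rare but significant | none |

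Four of the five named risks are grouped. Reading every preferred term under all eight groups finds no calcinosis, calciphylaxis or other calcification term. Table 5 shows no sign of redaction; the redacted entry in the SAP's list of tables falls between Tables 3 and 5.

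**Step 2: look for the pooled count elsewhere.** Tables 3.2.21 to 3.2.26 and Listing 2.7.7 cover sponsor-defined clinically notable events only. Protocol 9.5 (Events of Clinical Interest) is marked not applicable. No other table in SAP 8.2.3 or Appendix A pools mineralization terms.

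**Step 3: see what the ungrouped tables give.** The tables by system organ class and preferred term cover any event (3.2.2, 3.2.3), maximum severity (3.2.4), Grade 3 or higher (3.2.6, 3.2.7), serious (3.2.8, 3.2.9), related (3.2.10, 3.2.11), fatal (3.2.16), and reduction, interruption and discontinuation (3.2.18 to 3.2.20). Each would show calcinosis and calciphylaxis as separate rows where they occur. The rows cannot simply be added. For a set of terms, the number of participants with at least one event satisfies

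largest single-term count ≤ participants with any term ≤ sum of the term counts.

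One participant with both terms produces a 1 in each of two rows, and so do two participants with one term each. The rows are the same, but the pooled count is 1 in the first case and 2 in the second. A system organ class row does not settle this, because it also counts unrelated terms in that class.

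**Step 4: gauge the size.** The documents give no incidence, so the rates p below are assumptions. N = 164 is the planned enrolment in Protocol Table 2 (82 in Cohort A, up to 82 in Cohort B). Expected cases = N × p. P(at least 1) = 1 − (1 − p)^164.

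| Assumed p | Expected cases | P(at least 1) | P(at least 2) |
|---|---|---|---|
| 0.5% | 164 × 0.005 = 0.8 | 0.56 | 0.20 |
| 1% | 164 × 0.01 = 1.6 | 0.81 | 0.49 |
| 2% | 164 × 0.02 = 3.3 | 0.96 | 0.84 |
| 3% | 164 × 0.03 = 4.9 | 0.99 | 0.96 |

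N is close to a ceiling: Cohort B may enrol fewer than 82, and Cohort A can close after a futility look at about 25 evaluable participants. The realistic expectation is a handful of cases or none.

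**The case against.** The strongest reply is that nothing is hidden. Every breakdown in the six grouped tables also exists by preferred term, and Listings 2.7.1 to 2.7.6 carry the individual events. With zero to two cases, as expected at 0.5% or 1%, a reader can count participants from the adverse event listing. SAP 8.1 even allows a sparse frequency table to be replaced by a listing. All of this stands. A reader might infer that mineralization events would go unreported or that a signal would be lost; the documents do not support either reading. Only the planned participant-level count and its breakdowns are absent.

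A second reply is that no commitment is broken. Protocol 10.4.3 requires tabulation by preferred term and system organ class, which the SAP provides. The sentence in SAP 8.2.2 describes the groups and does not promise one for every risk of interest, and the groups are the sponsor's to define. This also stands: the gap is an inconsistency of coverage, not a breach of the protocol.

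Third, one might read Protocol 2.3 as naming exactly two rare but significant risks. Its wording introduces examples and is not exhaustive, so the point should not rest on that count.

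Finally, a loosely drawn group could do harm. Exclusion criterion 12 itself separates systemic ectopic calcification from common incidental calcification, and a row that mixed the two would blur the drug-related risk. That is a reason for care in choosing terms. It does not justify having no group at all.

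**Conclusion.** The point holds as a minor gap in safety reporting. Table 5 groups four of the five risks named in Protocol 2.3 and omits soft tissue mineralization, and the SAP gives no reason. As written, the plan would tabulate and list individual terms but would not report how many participants had at least one mineralization event, overall or by Grade 3 or higher, seriousness or dose action.

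The omission follows from the text alone and depends on no assumed rate. Its practical size does depend on one: about 0.8 to 4.9 expected cases at assumed rates of 0.5% to 3% in at most about 164 treated participants. At the low end pooling changes almost nothing. It helps only if several cases occur and are spread over more than one term, and the documents do not say how likely that is. No efficacy result and no single preferred-term incidence is affected.

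**What to change.** Before database lock, add a row 'Soft tissue mineralization' to SAP Table 5, defined by MedDRA v26.0 preferred terms covering at least calcinosis and calciphylaxis. Sponsor safety review should set the full list and keep out incidental calcifications of the kind excepted in exclusion criterion 12. The row then flows into Tables 3.2.21 to 3.2.26 and Listing 2.7.7 with no new data collection or method. Record the change in SAP 10.2. If the omission is deliberate, one sentence in SAP 8.2.2 giving the reason would close the point.

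The cost is a short term-selection review and one more row that may hold few or no events.

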8.2.3. Adverse Event Summaries

An overall summary of AEs by cohorts will include the following:

- Number (%) of participants who had any TEAEs
- Number (%) of participants who had any serious TEAEs
- Number (%) of participants who had any Grade 3 or higher TEAEs
- Number (%) of participants who had any TEAEs related to pemigatinib
- Number (%) of participants who temporarily interrupted pemigatinib because of TEAEs
- Number (%) of participants who permanently discontinued pemigatinib because of TEAEs
- Number (%) of participants who had pemigatinib dose reductions because of TEAEs
- Number (%) of participants who had any fatal TEAEs

The following summaries will be produced by MedDRA term:

- Summary of TEAEs by MedDRA SOC and PT
- Summary of TEAEs by MedDRA PT in decreasing order of frequency
- Summary of TEAEs by MedDRA SOC, PT, and maximum severity
- Summary of Grade 3 or higher TEAEs by MedDRA SOC and PT
- Summary of Grade 3 or higher TEAEs by MedDRA PT in decreasing order of frequency

- Summary of serious TEAEs by MedDRA SOC and PT
- Summary of serious TEAEs by MedDRA PT in decreasing order of frequency
- Summary of pemigatinib treatment-related TEAEs by MedDRA SOC and PT
- Summary of pemigatinib treatment-related TEAEs by MedDRA PT in decreasing order of frequency
- Summary of Grade 3 or higher pemigatinib treatment-related TEAEs by MedDRA SOC and PT
- Summary of pemigatinib treatment-related serious TEAEs by MedDRA SOC and PT
- Summary of TEAEs with a fatal outcome by MedDRA SOC and PT
- Summary of TEAEs leading to pemigatinib dose reduction by MedDRA SOC and PT
- Summary of TEAEs leading to pemigatinib dose interruption by MedDRA SOC and PT
- Summary of TEAEs leading to discontinuation of pemigatinib by MedDRA SOC and PT
- Summary of sponsor-defined clinically notable TEAEs by category and PT
- Summary of Grade 3 or higher sponsor-defined clinically notable TEAEs by category and PT
- Summary of serious sponsor-defined clinically notable TEAEs by category and PT
- Summary of sponsor-defined clinically notable TEAEs leading to pemigatinib dose reduction by category and PT
- Summary of sponsor-defined clinically notable TEAEs leading to pemigatinib dose interruption by category and PT
- Summary of sponsor-defined clinically notable TEAEs leading to discontinuation of pemigatinib by category and PT

